If patient qualifies for study, SC will describe study protocol and get verbal consent for study participation using the consent script. All patients will be sent a hard copy of the consent document for their records (available in English and Spanish) electronically along with the study surveys via RedCap.

Patients who decline will be excluded from study. Study participation status will be recorded in RedCap (including reason for declining participation).

Patients who decline to be in the study will be sent an appointment letter and will continue with scheduled genetic counseling appointment as per normal clinic protocol, not as part of the study.

**Pre-Appointment Resources and Survey Completion.** Patients who agree to participate in the study will be sent the pre-appointment survey (Appendix B). A Spanish version of the survey will be sent to Spanish-speaking patients. Surveys will include a hard copy of the consent document that can be downloaded as desired. Survey links will be sent to patients via email. All surveys will be available through REDCap.

The pre-appointment survey will consist of the Multi-dimensional Model of Informed Choice (MMIC) assessment and the Genomics Outcome Scale (GOS).

SC will check pre-appointment survey completion status two business days prior to appointment.

Patients with incomplete pre-appointment surveys will be contacted two business days prior to appointment and will be reminded to complete survey. Patients will be offered the option to complete survey via telephone with SC. Spanish-speaking patients will be contacted with an interpreter.

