## Form A

IRB #	STU -----
-------	-----------

SC will attempt to contact patients who cannot be reached the following business day.

Patients who do not complete pre-appointment survey will be excluded from study but will continue with scheduled genetic counseling appointment as standard of care.

Pre-appointment survey completion status and survey completion method will be recorded in RedCap by SC.

Genetic Counseling and Genetic Testing. Patients who are unable to watch the educational video prior to, or during their genetic counseling visit will be excluded from the study. They will still continue with their appointment, but not through the study. Patients excluded for this reason will be recorded in RedCap by SC.

Sample failure and test completion status will be recorded in RedCap by SC. Failure to complete testing will not exclude patient from the study itself.

Post-Appointment Survey and Study Incentive. SC will send post-appointment survey within 24 hours of GC appointment. A Spanish version of the survey will be sent to Spanish-speaking patients.

The post-appointment survey will consist of the Multi-dimensional Model of Informed Choice (MMIC) assessment, the Genetics Outcome Scale (GOS) and the Genetic Counseling Satisfaction Scale (GCSS).

SC will monitor survey completion status. Those with incomplete post-appointment surveys will receive reminder two business days post-appointment and will be offered option to complete the survey via telephone with SC.

If patient is not reached, SC will attempt to contact patient the following day (three business days post-appointment).

Those with incomplete surveys one week after the genetic counseling appointment will be excluded from study. This data will be recorded in RedCap.

Those who complete study surveys will be sent a \$15 gift card electronically.

Location/Setting. For IPGC, patients will be seen within PHHS/JPS clinics. Spanish translation services are provided through PHHS and JPS for patients in their institutions. TGC patients will not be required to be in a certain environment, but we anticipate they will be in their homes or workplace in a secure, private location. GCs will either be in a HIPPA compliant setting offsite or within a UTSW workspace for TGC visits.

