Data Analysis. Our primary study outcomes are to compare change in knowledge pre and post visit (through MMIC knowledge questions), patient satisfaction with GC visit after completion (GCSS) and genetic counseling visit completion rate between IPGC and TGC. Secondary objectives include comparison of empowerment score (GCOS), informed choice (MMIC scale), genetic testing completion, and cancelation/failure rates between the arms.

To evaluate intervention effects, we will conduct univariable and multivariable analysis for comparisons of each outcome of interest between intervention (TGC) and control group (IPGC). For the survey data, we will examine the data from each survey as well as total score or overall index of multiple questionnaires and compare them between the two study arms. We will perform linear regression models for continuous outcomes (e.g., total score of questionnaires) and logistic regression models for binary outcomes that are based on binary response (e.g., visit completion rates, test cancelation/failure and test completion rates). To compare binary outcomes between arms (such as visit completion rate), we will test by comparing rates of each arm via Chi-squared analysis and control for potential confounders. Potential covariates under consideration (e.g., age, race, sex, language, etc.) will be assessed as necessary and adjusted in multivariable models accordingly. We will evaluate whether there is any evidence of multi-collinearity issues among these variables to be adjusted in the model. Possible effect modifiers of intervention effects will be also evaluated by testing interactions (e.g., sex) and addressed to develop the final multivariable models, as well as reporting the intervention effect stratified as an effect modifier. Underlying assumptions of aforementioned regression models including linearity of associations will be also evaluated. We will examine dropouts or missing data to be able to identify accurate missing data mechanisms and select the best statistical approach. All analyses will be performed using SAS 9.4 (SAS Institute Inc, Cary, NC) at a statistical significance level of  $p=0.05$ .

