We anticipate a post-enrollment dropout (failure to complete the surveys) rate of 30% given our work with the underserved population. We plan to enroll 280 patients at a 1:1 ratio per arm (100 individuals enrolled per arm), expecting 200 to complete measured responses. We will monitor the dropout rate after the initial 50 individual responses are completed and adjust accrual for study-specific dropout until we have 200 participants' complete measured responses. With 200 patients we will enroll, we can detect mean differences of 0.398 standard deviation (SD) between two study arms with 80% power at a significance level of 0.05 (Table 1). For example, assuming SD of 2 for the GCSS, we will be able to detect a minimum difference of 0.8 ( $=0.398*2$ ) between two study arms with 100 participants enrolled per arm. For GCOS, assuming SD of 46.58, we will be able to detect a minimum difference of 18.54 between pre- and post-visit scores. For visit completion as the primary binary outcome variable, we will be able to detect a minimum difference of 18.6% assuming 63% in the control group, e.g., 81.6% (intervention) vs. 63% (control) with 80% power at significance level of 0.05. Of note, previously published outcomes and unpublished internal data will serve as a baseline for the study population.

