**Form A**

IRB #	STU -----
-------	-----------

*Table 1.* Summary of instrumentation with objectives, measures and distribution plan. Summary of data analysis plan per primary and secondary objectives. Minimum detectable difference between two study arms with 80% power at 2-sided significant level of 0.05 (n=100 per arm)

Aims	Objective Type	Instrumentation	Outcome Measure	Distribution	Minimum Detectable Effect Size at 80% power
Aim 1: Patient Satisfaction	Primary	GCSS	Whole scale score	Post	+/-0.8 points, assuming SD = 2 
Aim 1: Knowledge	Primary	MMIC (8 knowledge questions)	Measure score difference from pre/post	Pre and Post	+/-2 points, assuming SD = 5.03
Aim 1: Informed Decision Making	Second	MMIC (entire measure)	Measure score difference from pre/post	Pre and Post	n/a
Aim 1: GC-specific empowerment	Second	GOS	Measure score difference pre/post	Pre and Post	+/-18.54 points, assuming SD = 46.58 
Aim 2: GC visit completion	Primary	Database query	Proportion of visits scheduled and completed	n/a	18.6%, assuming 63% in control group 
Aim 2: Genetic test completion	Second	Database query	Proportion of genetic tests completed w/n 60d of visit	n/a	19.4%, assuming 77.4% in control group 
Aim 2: Genetic test cancellation/failure	Second	Database query	Proportion of genetic tests initiated compared to tests canceled/failure	n/a	15%, assuming 9% in control group 

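### The gift card depends on a survey that rates the completed visit, so it indirectly rewards attendance, a primary outcome, in both arms

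*Combined protocol and SAP*

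**What the plan says.** All references are to Form A, item 4.a, of the combined protocol and SAP.

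- **Payment.** Under Post-Appointment Survey and Study Incentive: "Those who complete study surveys will be sent a" 15-dollar electronic gift card. The plan has two surveys, one before and one after the appointment.
- **Timing of the second survey.** "SC will send post-appointment survey within 24 hours of GC appointment". It holds the MMIC, the GOS and the GCSS.
- **What the GCSS rates.** Data Analysis lists among the primary outcomes "patient satisfaction with GC visit after completion (GCSS) and genetic counseling visit completion rate between IPGC and TGC". The satisfaction score therefore presupposes a visit that took place.
- **The attendance outcome.** Table 1 measures it as "Proportion of visits scheduled and completed", by database query. The sample size text says "we will be able to detect a minimum difference of 18.6% assuming 63% in the control group", with the example "81.6% (intervention) vs. 63% (control) with 80% power at significance level of 0.05".
- **Exclusion.** Patients whose surveys are still incomplete one week after the appointment are excluded from the study.
- **Contact before the visit.** The coordinator calls one week ahead to check eligibility and obtain verbal consent. Later, "Patients with incomplete pre-appointment surveys will be contacted two business days prior to appointment and will be reminded to complete survey".

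No section says whether a patient who misses the visit is sent the second survey, and none considers the effect of the card on attendance.

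**The concern.** A reward that in practice requires attendance is attached to a trial in which attendance is a primary outcome, in a population selected for being indigent. Two things are at stake.

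The first is transfer to practice. Item 1 gives the purpose as a framework for genetic service delivery in these populations nationally. Completion rates obtained with a card in prospect may sit above those of routine care without one. They may also fit the 63% planning rate poorly, if that rate came from unpaid patients.

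The second is the contrast. The planning rates leave more non-attenders to move in the in-person arm (37%) than in the telephone arm (18.4%), so the card could change the difference between arms even though the offer is identical.

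A related problem is that the same survey governs exclusion. Read literally, a no-show has no post-visit survey, is excluded after one week, and may drop out of the analysis of the outcome that the no-show defines.

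**Working it through.** **1. The plan's own figure.** Inputs from the sample size text and Table 1: p1 = 0.63, p2 = 0.816, n = 100 per arm, two-sided 0.05, 80% power. With pooled variance under the null and continuity correction,

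z = [(p2 − p1 − 1/n) − 1.96·√(2·p̄(1 − p̄)/n)] / √(p1(1 − p1)/n + p2(1 − p2)/n)

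p̄ = 0.723. Numerator: 0.176 − 1.96 × 0.0633 = 0.176 − 0.1240 = 0.0520. Denominator: 0.0619. z = 0.839, so power is 79.9%. Solving for 80% power gives a detectable difference of 18.6 points, as stated. Without the correction the detectable difference is 17.7 points and power at 18.6 points is 84.2%. The plan's figure is therefore the continuity-corrected one, and it is not in dispute.

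**2. Is attendance a condition of payment?** The card requires the study surveys, the second survey is timed from the appointment, and one of its three instruments rates the completed visit. The plan provides no version for a patient who did not attend. Attendance is thus necessary in practice. It is not sufficient: an attender who leaves a survey incomplete gets no card.

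**3. What the card could do to the contrast.** The documents give no figure for response to the card. Assume, for illustration only, that it brings in the same share s of would-be no-shows in each arm. Then control = 0.63 + 0.37s, telephone = 0.816 + 0.184s, and difference = 0.186 × (1 − s).

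| s | In person | Telephone | Difference (points) | Power, corrected | Power, uncorrected |
|---|---|---|---|---|---|
| 0 | 63.0% | 81.6% | 18.6 | 79.9% | 84.2% |
| 10% | 66.7% | 83.4% | 16.7 | 73.4% | 78.6% |
| 20% | 70.4% | 85.3% | 14.9 | 65.9% | 72.0% |
| 30% | 74.1% | 87.1% | 13.0 | 57.6% | 64.6% |

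If the arms do not truly differ, an equal s leaves the difference at zero.

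**4. Direction if the response is unequal.** The contrast widens when 0.184 × s(telephone) exceeds 0.37 × s(in person), that is, when the telephone share is more than about twice the in-person share (0.37/0.184 = 2.01). For example, with 10% in person and 30% by telephone, the rates are 0.63 + 0.037 = 66.7% and 0.816 + 0.0552 = 87.1%, a difference of 20.4 points. The documents exclude neither direction.

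**5. Detectable difference at higher control rates.** On the plan's continuity-corrected basis, n = 100 per arm: 15.8 points at 75% control and 12.2 points at 85%. (Uncorrected: 15.0 and 11.4.)

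**6. Cost of paying no-shows.** 280 enrolled at 1:1 is 140 per arm. Expected no-shows at the planning rates: 140 × 0.37 + 140 × 0.184 = 51.8 + 25.8 = 77.6, about 78 cards. 77.56 × 15 = about 1,163 dollars.

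**The case against.** The strongest defence is that the plan pays for returned surveys, under one rule and at one amount in both arms, which is an ordinary choice for a pilot with an expected 30% survey dropout. Most of this stands. A reader might infer that the study pays patients to attend. The documents do not say so: the card is for surveys, and the dependence on attendance is inferred from the timing and the GCSS.

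A reader might also infer that the card biases the comparison, or that it must shrink the difference because the in-person arm has more non-attenders. Neither follows. An identical offer creates no difference by itself, and shrinkage needs an assumption about relative response. A small card could move more people to take a call than to travel, as step 4 of the working shows.

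A third tempting reading is that the trial becomes unworkable once control attendance passes 81.4%, because adding 18.6 points would exceed 100%. That mistakes a minimum detectable difference for a gain that must occur. The detectable difference falls as the control rate rises.

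Further limits also stand:

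- The card can act only on patients who know of it before the visit, and the consent text is not in the copy reviewed.
- Whether the 63% came from unpaid patients is not stated.
- Randomization and scheduling precede the consent call. If the denominator is every scheduled patient, those not reached or declining never faced the offer.
- The pre-visit calls are described as eligibility, consent and survey contacts, not attendance reminders. Separating the card from attendance would leave them in place.

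What the defence does not answer is that the plan ties a reward to attendance in practice, makes attendance a primary outcome, and does not mention the link.

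**Conclusion.** The point holds as a design weakness that is inexpensive to remove. It is not an error in the plan's arithmetic and not a demonstrated bias between arms. Payment depends in practice on attendance, so the card indirectly rewards visit completion in both arms. It may raise completion above routine care and may change the contrast. The reduction from 18.6 to between 16.7 and 13.0 points, with power falling from 79.9% to between 73.4% and 57.6%, rests wholly on the assumed equal conversion of 10% to 30% of no-shows. It also takes the example rates of 63% and 81.6% as the rates without a card. The actual size and direction cannot be derived from the documents.

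The exclusion of patients without a post-visit survey, together with an undefined visit-completion population, is probably the larger threat to this outcome, and should be settled in the same edit.

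**What to change.** In item 4.a, Post-Appointment Survey and Study Incentive:

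1. Send enrolled patients who miss the visit the post-appointment survey without the GCSS.
2. Give the card for completing the surveys sent, whether or not the visit took place, and state this in the consent script.

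In item 4.a, Data Analysis and sample size:

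3. Define the visit-completion population. Count no-shows as not completed, and do not exclude them from that analysis for lack of a post-visit survey.
4. Do not count surveys from no-shows towards the 200 complete responses, since they carry no satisfaction score and no change across a visit.
5. If detectable differences at higher control rates are added to Table 1, use the basis of the existing 18.6-point row: 15.8 points at 75% control and 12.2 at 85%.

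The cost is about 78 further cards, about 1,163 dollars, at 280 enrolled and the planning rates, if every no-show completes the surveys. It rises if accrual is extended to reach 200 complete responses. Coordinator time to contact no-shows and a sentence in the consent script come on top.

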### 3. Study Design.

[figure not shown]
Describe the study design (e.g., single/double blind, parallel, crossover, etc.) Consider inserting a scheme to visually present the study design.

This is a two-arm parallel randomized controlled study of IPGC vs. TGC with two enrolling sites.

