**Randomization and Scheduling:**

Study coordinator (SC) will monitor referral queue daily

Randomization software (<http://abtesting.ideas42.org/randomize/>) will be used to randomize patients in the referral queue to each study arm (in-person genetic counseling or IPGC/ telephone genetic counseling or TGC). Patients who meet the following exclusion criteria will not be randomized to a study arm. Patients who are excluded from the study will be scheduled for an appointment as per normal clinic protocol by the clinic schedulers.

SC will monitor number of participants per study arm and adjust recruitment accordingly.

Patients who have been randomized to a study arm will be scheduled for IPGC or TGC by schedulers at John Peter Smith (JPS) and Parkland Hospital (PHHS). Schedulers will inform patients of their appointment as per normal clinic protocol. Spanish-speaking patients will be contacted with an interpreter.

Patients who elect alternative service delivery model for genetic counseling than what was assigned after randomization will be excluded from the study. The genetic counseling appointment type will be modified based on patient preference and patient will continue with scheduled visit, but not as part of the study.

SC will record the following data for all referred patients in Research Electronic Data Capture (RedCap), a secure, web-based application for research data: MRN; study arm assigned; genetic counseling appointment date; if patient was excluded from study, and reason for exclusion. The following demographic data will also be tracked: patient's age; patient's sex; patient's race and ethnicity; patient's preferred language; patient's contact information (phone number and e-mail address)

**Study Eligibility Determination and Informed Consent.** One week prior to scheduled genetic counseling appointment, SC will call patient to assess if patient meets study eligibility criteria. Spanish-speaking patients will be contacted with an interpreter.

If SC cannot reach the patient, SC will make second contact attempt the following business day.

Scheduled patients who cannot be reached or do not call back will be excluded from study.

SC will record the following data in RedCap: contact date and outcome; if eligibility criteria were met; if patient was excluded from study, and reason for exclusion.

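### The plan does not say whether the same counselors serve both arms, records and models neither counselor nor site, and does not stratify by site, so a counselor effect could be inseparable from counseling mode.

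*Combined protocol and SAP*

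**What the plan says.** - **Design (section 3).** "This is a two-arm parallel randomized controlled study of IPGC vs. TGC with two enrolling sites".
- **Allocation (section 4.a, Randomization and Scheduling).** A web tool "will be used to randomize patients in the referral queue to each study arm". No strata or blocks are described. On balance, the text says only that "SC will monitor number of participants per study arm and adjust recruitment accordingly". Schedulers at both hospitals book visits of either type.
- **Delivery (section 4.a, Location/Setting).** "For IPGC, patients will be seen within PHHS/JPS clinics". For the other arm, "GCs will either be in a HIPPA compliant setting offsite or within a UTSW workspace for TGC visits". The number of counselors and how they are assigned are not given.
- **Recorded data (section 4.a).** The listed items include record number, assigned arm, appointment date, exclusions with reasons, demographics and preferred language. Neither counselor nor site is listed.
- **Analysis (section 4.a, Data Analysis).** Linear and logistic regression at patient level, with no clustering. The covariate list begins "Potential covariates under consideration (e.g., age, race, sex, language, etc" and is open-ended. Covariates are to be assessed and adjusted for only where judged necessary.
- **Outcomes (Table 1).** GCSS after the visit, change in MMIC knowledge, and visit completion are all primary.

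**The concern.** Randomizing patients does not randomize counselors. The two modes are run from different places, so a rota with one group on clinic visits and another on telephone visits is possible, and nothing in the text rules it out. Two things would follow from such a rota.

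First, the arm contrast would combine mode with the difference between two small groups of counselors. GCSS measures satisfaction with the counseling visit, so that difference would enter a primary outcome directly. It could create a mode effect or hide one, and the stated hypothesis of no significant difference in satisfaction and knowledge is exposed to both. No later adjustment could separate the two, because counselor would be nested within arm.

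Second, patients of the same counselor would be correlated, and regression that treats them as independent would give standard errors that are too small.

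Site raises a smaller question. With two hospitals booking visits, site may well predict visit completion, yet it is neither a stratification factor nor a named covariate.

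**Working it through.** **Inputs from the documents.** 100 analyzed per arm, two-sided 0.05, 80% power, detectable difference 0.398 SD; GCSS SD 2, so 0.8 points; visit completion 63% against 81.6%, a difference of 18.6 points (section 4.a and Table 1).

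**Inputs assumed.** Number of counselors per arm k, counselor ICC, the site split and the site difference in visit completion. The documents give none of these.

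**1. The plan's own figures.** For independent patients, SE = sqrt(2/100) = 0.141 SD. The normal approximation gives (1.960 + 0.842) × 0.141 = 0.396 SD, and the two-sample t-test gives 0.398 SD, as stated. The 18.6-point difference needs 101 per arm with a continuity correction and 90 without, so it is also reproduced closely. Neither figure allows for counselor or site.

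**2. Counselors specific to an arm (conditional case).** With m = 100/k patients per counselor:

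- Design effect: DE = 1 + (m − 1) × ICC
- True SE = sqrt(0.02 × DE)
- Actual rejection rate of the nominal 5% test with no mode effect = 2 × [1 − Φ(1.96/sqrt(DE))]

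| k per arm | ICC | DE | True SE (SD) | Rejection rate | Power at 0.398 SD, SE corrected |
|---|---|---|---|---|---|
| 4 | 0.02 | 1.48 | 0.172 | 10.7% | 64% |
| 4 | 0.05 | 2.20 | 0.210 | 18.6% | 48% |
| 2 | 0.02 | 1.98 | 0.199 | 16.4% | 52% |
| 2 | 0.05 | 3.45 | 0.263 | 29.1% | 33% |

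The power column uses normal critical values. With only 2k − 2 degrees of freedom between counselors (6 or 2 here), true power would be lower.

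The part of the arm difference due to counselors alone has SD sqrt(2 × ICC/k). This is sqrt(0.04/4) = 0.10 SD at the mild end and sqrt(0.10/2) = 0.22 SD at the severe end. On GCSS with SD 2, that is 0.2 to about 0.45 points, against a detectable difference of 0.8.

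The problem shrinks with more counselors or a lower ICC: with 10 per arm and ICC 0.01, DE = 1.09 and the rejection rate is 6.0%.

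**3. Counselors crossed with arm.** If each counselor sees similar proportions of both arms, counselor main effects cancel from the contrast. Its SE is then sqrt(0.02 × (1 − ICC)), which at ICC 0.05 is sqrt(0.019) = 0.138 SD. This is no larger than the planned 0.141. It assumes that counselors do not differ in how well they work in each mode.

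**4. Site.** Take simple randomization, 100 per arm and an even site split (assumed). The difference in site share between arms has SD sqrt(0.25 × 2/100) = 0.071, so its 95% range is ±1.96 × 0.071 = ±13.9 percentage points. That is imbalance in the covariate. If the sites differed by 20 points in visit completion (assumed), the arm contrast would move by 0.139 × 20 = 2.8 points at that limit, against the 18.6 points planned for.

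**The case against.** The strongest reply is that the concern is read from silence. The Location/Setting sentence on telephone visits says where counselors sit, not who serves which arm. A reader might infer from it that separate staff deliver the two arms. The documents do not say so, and they use one undifferentiated term for counselors. This stands: arm-specific staffing is a possibility, not a finding, and every rejection rate above depends on it.

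A reader might also infer that site or language differences could systematically pass for a mode effect. The documents do not support that. Patients are randomized individually, schedulers at both hospitals book both visit types, and chance imbalance is already inside the nominal 5% error rate. Preferred language is recorded and is a candidate covariate. Systematic site bias would need the undefined adjustment of recruitment, or later removals such as "Patients who elect alternative service delivery model for genetic counseling than what was assigned after randomization will be excluded from the study", to depend on both site and arm. Nothing shows that they do.

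Other parts of the reply stand in part. The covariate list is open, so site is not excluded, and it might be recoverable from the record number, though that is an inference. The standard session and shared video may reduce counselor variation, especially for knowledge, but they standardize content and not the person delivering it. The design figure and two passages are unavailable, so the statement covers the visible text only.

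What the reply does not meet is that no listed field identifies the counselor, and that if counselors were nested in arm no analysis could undo it.

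**Conclusion.** The concern holds in a limited form. The plan neither prevents counselors from being specific to an arm nor would detect it from the data it lists. Should that happen, mode and counselor could not be separated on GCSS. With 2 to 4 counselors per arm and ICC 0.02 to 0.05, all assumed, a nominal 5% test would reject about 11% to 29% of the time with no mode effect. If the same counselors serve both arms in similar proportions, the inflation largely disappears.

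For site, the lack of stratification and of a prespecified term costs precision and leaves some chance imbalance, worth at most about 2.8 points on visit completion under the assumptions above. It is not a source of systematic bias on the documents' evidence.

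This should be settled before enrollment, because the counselor rule and the counselor field have to be in place prospectively.

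**What to change.** 1. In Location/Setting, require each participating counselor to see patients in both arms, in similar proportions.
2. Add counselor and site as REDCap fields.
3. In Randomization and Scheduling, specify a concealed permuted-block list stratified by site.
4. In Data Analysis, make site and language prespecified covariates in every primary model, in place of adjustment as judged necessary.
5. Add counselor as a factor, or in a sensitivity analysis, for GCSS and knowledge. This helps only once item 1 is in force.

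The cost is rota wording, two data fields, a stratified list and a few lines of analysis text, with no extra staff. There are two small drawbacks. Counselors must split their sessions between modes. Stratifying at the referral queue also does not guarantee balance among those analyzed, because exclusions follow randomization, so the site term is still needed.

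### Optional improvement, not an error: name the pre-visit score as a covariate in the pre/post comparisons of knowledge (primary) and empowerment (secondary)

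*Combined protocol and SAP*

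**What the plan says.** All references are to the combined protocol and SAP, section 4.a unless stated.

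- **Outcome.** Data Analysis introduces the primary outcomes with "Our primary study outcomes are to compare change in knowledge pre and post visit (through MMIC knowledge questions". Table 1 defines primary knowledge as "Measure score difference from pre/post" and secondary empowerment as "Measure score difference pre/post". Data Analysis calls the empowerment instrument GCOS and Table 1 calls it GOS; I follow the Table 1 definition.
- **Model.** Continuous outcomes go into linear regression. For every outcome, "we will conduct univariable and multivariable analysis for comparisons of each outcome of interest". The text does not say which of the two is primary.
- **Covariates.** "Potential covariates under consideration (e.g., age, race, sex, language, etc.) will be assessed as necessary and adjusted in multivariable models accordingly". The list is open, and the pre-visit score is not among its examples.
- **Availability.** Both instruments are on the pre-appointment survey, and "Patients who do not complete pre-appointment survey will be excluded from study".
- **Planning figure.** With 100 per arm, 80% power and two-sided 0.05, the detectable difference is given as 0.398 SD.

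**The concern.** When a change score is compared between randomised arms and the pre-visit score is available, adding that score to the model normally narrows the interval for the arm effect without further data. Here the plan permits the adjustment but does not commit to it.

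Two things are at stake. First, precision: section 1 expects no significant difference in knowledge between arms, and such a result tells the reader more when the interval is narrow. Second, choice of estimate: if the arms differ at the pre-visit survey, the change estimate and the adjusted estimate differ too. With no primary model named, the choice between them could be made after the data are seen.

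**Working it through.** **1. The plan's own figure.** For a two-sample t-test without covariates, 100 per arm, 80% power and two-sided 0.05, the detectable difference is 0.3981 SD. The stated 0.398 reproduces.

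**2. Inputs not in the documents.** Let r be the correlation of pre- and post-visit scores and k = SD(post)/SD(pre). Neither is given, so both are varied as assumptions. The documents also do not say whether the planning SDs (5.03 for knowledge, 46.58 for empowerment) are SDs of change or of a single score. For that reason no gain in score points is given.

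**3. Precision.** With balanced pre-visit means,

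Var(adjusted)/Var(change) = k²(1 − r²)/(1 + k² − 2rk) = 1 − (1 − rk)²/(1 + k² − 2rk).

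This is at most 1, equals 1 when rk = 1, and reduces to (1 + r)/2 when k = 1. The excess width of the unadjusted interval is 1/√ratio − 1. Example at k = 0.8, r = 0.5: 0.64 × 0.75/(1.64 − 0.80) = 0.48/0.84 = 0.571, and 1/√0.571 − 1 = 32%.

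| | r = 0.3 | r = 0.5 | r = 0.7 | r = 0.9 |
|---|---|---|---|---|
| k = 1: ratio (excess width) | 0.650 (24%) | 0.750 (15%) | 0.850 (8%) | 0.950 (3%) |
| k = 0.8: ratio (excess width) | 0.502 (41%) | 0.571 (32%) | 0.628 (26%) | 0.608 (28%) |
| k = 1.25: ratio (excess width) | 0.784 (13%) | 0.893 (6%) | 0.981 (1%) | 0.950 (3%) |

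Simulation of 4,000 trials with 100 per arm agreed with these ratios to within 0.021. A high correlation makes the gain small at k = 1, but not at k = 0.8.

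**4. Cost of adjusting.** With balanced pre-visit means the cost is one degree of freedom. With an imbalance of d SD, the variance of the adjusted estimate is inflated by about 1 + d²/4.

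- d = 0.2: 1 + 0.04/4 = 1.01, which is negligible.
- d = 0.5: 1 + 0.25/4 = 1.0625. The ratio then becomes 0.950 × 1.0625 = 1.009 at k = 1, r = 0.9, and 0.981 × 1.0625 = 1.042 at k = 1.25, r = 0.7. The second is a loss of about 2% in width (√1.042 = 1.021).

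So a large imbalance can slightly outweigh the gain, but only when rk is near 1.

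**5. Difference between the two estimates.** If D is the arm difference in pre-visit means and b the fitted slope, adjusted minus change = (1 − b)D. By chance alone, D stays within 1.96 × √(2/100) = 0.28 SD in 95% of trials with 100 per arm. Take D = 0.2 SD as an assumption. With equal variances b = r, and the estimates differ by 0.2 × (1 − r) = 0.14, 0.10, 0.06 and 0.02 SD at r = 0.3, 0.5, 0.7 and 0.9. These values need k = 1; in general b = rk.

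**6. Timing of the pre-visit survey.** The survey follows arm assignment. Section 4.d has telephone patients view the video before or during the visit, and the available text does not fix its order relative to the survey. As a check, suppose that the telephone arm's pre-visit score is raised by 0.5 SD, there is no true effect on the post-visit score, r = 0.5 and k = 1. The mean estimates are then −0.50 SD for change, −0.5 × 0.5 = −0.25 SD for the adjusted model, and 0.00 for the post-visit score alone.

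**The case against.** The strongest reply is that this is a preference. The study is a pilot, unadjusted change is valid under randomisation, the power figure matches it, and the open covariate list already allows the adjustment. All of that stands, and it is why the point is optional. It does not answer the suggestion itself: an allowed adjustment is not a prespecified one, and the data are already collected.

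A second reply is that the gain is unknown. That stands too. Over the values tabulated the excess width runs from 1% to 41%, and it is zero when rk = 1.

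A third reply is that the pre-visit score may itself be affected by arm, so adjusting for it is unsafe. In the check above the adjusted model is indeed biased, but by half as much as the planned change comparison, so this does not favour leaving the plan as it is. It does justify a sensitivity analysis without the pre-visit score. A reader might go further and infer that the telephone arm's scores will be contaminated by the video. The documents do not support that: survey completion is checked two business days before the visit, no time is given for sending the video, and the design figure is not available.

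**Conclusion.** The point holds as a free improvement of low priority. Under assumed equal SDs, the planned change comparison gives intervals about 24% to 3% wider than needed as r goes from 0.3 to 0.9. The range is 41% to 26% at k = 0.8 and 13% to 1% at k = 1.25. These figures assume balanced pre-visit means and values of r and k that the documents do not supply.

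Three stronger readings are tempting and are not supported:

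- That the change analysis or the 0.398 SD is wrong. The analysis is valid and the figure reproduces.
- That the plan rules out adjustment. Its covariate list is open.
- That adjustment would deal with the exclusions after randomisation. The plan removes patients who choose the other mode ("Patients who elect alternative service delivery model for genetic counseling than what was assigned after randomization will be excluded from the study") and those with late surveys ("Those with incomplete surveys one week after the genetic counseling appointment will be excluded from study"). Selection from these rules is a separate matter that a pre-visit covariate does not repair.

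**What to change.** Before data review, add to Data Analysis in section 4.a:

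- The primary analysis of knowledge is a linear regression of the post-visit score on arm and pre-visit score, in all analysed patients. Using change as the response with the same two terms gives the same arm estimate and standard error. The empowerment score (GOS/GCOS) is analysed with the same form of model.
- A comparison of post-visit scores by arm without the pre-visit score, in the same patients, is a sensitivity analysis only. It does not depend on when the pre-visit survey was answered.

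The cost is about two sentences. It needs no extra patients, no new data field and no change to study conduct, and the stated sample size can stay as it is.
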